Submit required forms and documents to the CTSU Regulatory Office using the Regulatory Submission Portal on the CTSU website.

To access the Regulatory Submission Portal log in to the CTSU members' website, go to the Regulatory section and select Regulatory Submission.

Institutions with patients waiting that are unable to use the Regulatory Submission Portal should alert the CTSU Regulatory Office immediately at [name] in order to receive further instruction and support.

Checking Your Site's Registration Status:

You can verify your site registration status on the members' section of the CTSU website.

- Log on to the CTSU members' website;
- Click on *Regulatory* at the top of your screen;
- Click on *Site Registration*;
- Enter your 5-character CTEP Institution Code and click on Go

NOTE: The status shown only reflects compliance with site registration requirements as outlined above. It does not reflect compliance with protocol requirements for individuals participating on the protocol or the enrolling investigator's status with the NCI or their affiliated networks.

Patient Enrollment

Patients must not start protocol treatment prior to randomization.

Treatment should start within 7-10 working days after randomization.

Randomization

Please note that no blinded starter supplies will be available for this study. At the time of patient randomization each patient will be assigned a specific blinded drug ID number (e.g. DR117). This blinded drug ID number should be included on the drug request form that is submitted to the ECOG-ACRIN Drug Team. (See Section [0](#) for complete details.)

NOTE: When a patient has been successfully randomized, the confirmation of randomization will indicate that the patient is on Arm X. The patient will actually be randomized to Arm A or B, but as this is a double-blind trial, that information cannot be displayed.

The Oncology Patient Enrollment Network (OPEN) is a web-based registration system available on a 24/7 basis. OPEN is integrated with CTSU regulatory and roster data and with the Lead Protocol Organization (LPOs) registration/randomization systems or Theradex Interactive Web Response System (IWRS) for retrieval of patient registration/randomization assignment. OPEN will populate the patient enrollment data in NCI's clinical data management system, Medidata Rave.

Requirements for OPEN access:

- A valid CTEP-IAM account;
- To perform enrollments or request slot reservations: Be on a LPO roster, ETCTN Corresponding roster, or PO roster with the role of Registrar. Registrars must hold a minimum of an AP registration type;
- Have an approved site registration for a protocol prior to patient enrollment.

To assign an Investigator (IVR) or Non-Physician Investigator (NPIVR) as the treating, crediting, consenting, drug shipment (IVR only), or receiving investigator for a patient transfer in OPEN, the IVR or NPIVR must list the IRB number used on the site's IRB approval on their Form FDA 1572 in RCR. If a DTL is required for the study, the IVR or NPIVR must be assigned the appropriate OPEN-related tasks on the DTL.

Prior to accessing OPEN, site staff should verify the following:

- Patient has met all eligibility criteria within the protocol stated timeframes; and
- All patients have signed an appropriate consent form and HIPAA authorization form (if applicable).

NOTE: The OPEN system will provide the site with a printable confirmation of registration and treatment information. Please print this confirmation for your records.

Access OPEN at <https://open.ctsu.org> or from the OPEN link on the CTSU members' website. Further instructional information is in the OPEN section of the CTSU website at <https://www.ctsu.org> or <https://open.ctsu.org>. For any additional questions, contact the CTSU Help Desk at [name] or [contact].

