- _____ 3.1.18.3 Current clinically significant uncontrolled arrhythmias. Exception: Patients with controlled atrial fibrillation for >30 days prior to randomization are eligible.
- _____ 3.1.18.4 Acute coronary syndromes (including myocardial infarction and unstable angina), coronary angioplasty, or stenting within 6 months prior to randomization.
- _____ 3.1.18.5 Abnormal cardiac valve morphology (\geq grade 2) documented by echocardiogram unless a cardiologist concludes the valve abnormality is not clinically significant. Patients with grade 1 abnormalities (i.e., mild regurgitation/stenosis) are eligible.
- _____ 3.1.18.6 Patients with known history or current symptoms of cardiac disease, or history of treatment with cardiotoxic agents, should have a clinical risk assessment of cardiac function using the New York Heart Association Functional Classification. To be eligible for this trial, patients should be class 2B or better.

_____ 3.1.19 Patient must be able to swallow and retain oral medication and must not have any clinically significant gastrointestinal abnormalities that may alter absorption such as malabsorption syndrome or major resection of the stomach or bowels.

_____ 3.1.20 Patient with known serious concurrent infection or medical illness, including psychiatric disorders, which would jeopardize the ability of the patient to receive the treatment outlined in this protocol with reasonable safety are not eligible.

- _____ 3.1.21 Patient must not be receiving concurrent therapy for their tumor (i.e. chemotherapeutics or investigational agents). Radiotherapy delivered to palliate pain is allowed as long as it is not targeting a lesion that meets RECIST criteria for progression. Radiation therapy to the surgical bed with gamma knife radiotherapy while on treatment during the first cycle is allowed for small volume surgically resected brain metastases. Gamma knife radiotherapy for known active, asymptomatic small volume CNS lesions may be performed during the first cycle while on study. Radiotherapy for new CNS lesions identified beyond the first cycle is not allowed on study.
- _____ 3.1.22 Patient must not have a known immediate or delayed hypersensitivity reaction or idiosyncrasy to drugs chemically related to study drug, or excipients or to dimethyl sulfoxide (DMSO).

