5.1.6 Concomitant Medication and Procedures
Because HCQ has known effects on P450 enzymes, patients requiring anti-convulsants may be treated with any of the non-enzyme inducing anti-convulsants which include: felbamate, valproic acid, gabapentin, lamotrigine, tiagabine, topiramate, or levetiracetam. The exception is zonisamide which should be avoided, as zonisamide accumulates in red blood cells as does HCQ. For nausea, aprepitant should be avoided. Radiation therapy to the surgical bed with gamma knife radiotherapy while on treatment during the first cycle is allowed for small volume surgically resected brain metastases. Gamma knife radiotherapy for known active, asymptomatic small volume CNS lesions may be performed during the first cycle while on study. If radiotherapy is being delivered while the patient is on study, patients should hold all three study medications for 2 days prior to radiation and resume study medication one day after completion of radiation. Radiotherapy for new CNS lesions identified beyond the first cycle is not allowed on study. All other concomitant medications are permitted.

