6.1.2 Disease Parameters

Measurable Disease

Measurable lesions are defined as those that can be accurately measured in at least one dimension (longest diameter to be recorded) as ≥ 20 mm by chest x-ray, as

≥ 10 mm with CT scan, or ≥ 10 mm with calipers by clinical exam. All tumor measurements must be recorded in millimeters.

NOTE: Tumor lesions that are situated in a previously irradiated area might or might not be considered measurable. If the investigator thinks it appropriate to include them, the conditions under which such lesions should be considered must be defined in the protocol.

Malignant Lymph Nodes

To be considered pathologically enlarged and measurable, a lymph node must be

≥ 15 mm in short axis when assessed by CT scan (CT scan slice thickness recommended to be no greater than 5 mm). At baseline and in follow-up, only the short axis will be measured and followed.

Non-measurable Disease

All other lesions (or sites of disease), including small lesions (longest diameter < 10 mm or pathological lymph nodes with ≥ 10 to < 15 mm short axis), are considered non-measurable disease. Bone lesions, leptomeningeal disease, ascites, pleural/pericardial effusions, lymphangitis cutis/pulmonitis, inflammatory breast disease, and abdominal masses (not followed by CT or MRI), are considered as non-measurable. Non-measurable also includes lesions that are < 20 mm by chest x-ray.

NOTE: Cystic lesions that meet the criteria for radiographically defined simple cysts should not be considered as malignant lesions (neither measurable nor non-measurable) since they are, by definition, simple cysts.

'Cystic lesions' thought to represent cystic metastases can be considered as measurable lesions, if they meet the definition of measurability described above. However, if non-cystic lesions are present in the same patient, these are preferred for selection as target lesions.

Target Lesions

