All measurable lesions up to a maximum of 2 lesions per organ and 5 lesions in total, representative of all involved organs, should be identified as target lesions and recorded and measured at baseline. Target lesions should be selected on the basis of their size (lesions with the longest diameter), be representative of all involved organs, but in addition should be those that lend themselves to reproducible repeated measurements. It may be the case that, on occasion, the largest lesion does not lend itself to reproducible measurement in which circumstance the next largest lesion which can be measured reproducibly should be selected.

A sum of the diameters (longest for non-nodal lesions, short axis for nodal lesions) for all target lesions will be calculated and reported as the baseline sum diameters. If lymph nodes are to be included in the sum, then only the short axis is added into the sum. The baseline sum

of the diameters will be used as reference to further characterize any objective tumor regression in the measurable dimension of the disease.

Non-target Lesions

All other lesions (or sites of disease) including any measurable lesions over and above the 5 target lesions should be identified as non-target lesions and should also be recorded at baseline. Measurements of these lesions are not required, but the presence or absence of unequivocal progression of each should be noted throughout follow-up.

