7.1 Therapeutic Parameters

1. Prestudy CXR and/or scans should be done ≤ 3 weeks prior to randomization.
2. Prestudy CBC (with differential and platelet count) should be done ≤ 14 days prior to randomization.
3. All required prestudy chemistries, as outlined in Section [Q](#), should be done ≤ 14 days prior to randomization.

Assessment	Baseline	X= Each 28-day Cycle (Monthly) ¹ /alternative interval	End of treatment ⁷ (for any reason) or disease progression	Post Treatment/ Follow- up ⁶
History and physical examination	X	X		
Vital Signs (including BP)	X	X		
EKG	X	X		
LVEF	X			
Standard ophthalmological exam ¹⁰	X	Yearly or as clinically indicated		
Transthoracic echo ⁸	X	Every 3 months or as clinically indicated	As clinically indicated	As clinically indicated
Brain CT or MRI	X	Every 4 cycles if brain metastases are present on baseline scan, or more often as clinically indicated	As clinically indicated	As clinically indicated
Chest CT ²	X	Every 2 cycles or more often as clinically indicated. Confirmatory scans at least 4 weeks following initial documentation of objective response ⁹	As clinically indicated	Every 2 months until 6 months after completion of study treatment and as clinically indicated per protocol Section 5.4.3.11 for cuSCC risk management
Abdomen/pelvis CT or MRI ²	X	Every 2 cycles and as clinically indicated Confirmatory scans at least 4 weeks	As clinically indicated	As clinically indicated

Assessment	Baseline	X= Each 28-day Cycle (Monthly) ¹ /alternative interval	End of treatment ⁷ (for any reason) or disease progression	Post Treatment/ Follow- up ⁶
		following initial documentation of objective response ⁹		
CBC with differential ⁴	X	X	X	
Serum chemistry ⁵	X	X	X	
PT/PTT ⁹	X	X		
Serum or Urine Pregnancy Test ³	X			
Biological Sample Submissions		See Sections 7.2 and 0		

1. Day 1 of cycle 1 begins the first day of treatment. A cycle constitutes 28 days or 4 weeks of D+T+HCQ/ placebo therapy. Monthly tests and procedures should be done on Day 1 of each cycle, however, account for major holidays and unforeseen events such as inclement weather, scheduled visits and testing can occur +/- 1 week from the start of each cycle, as long as there is documentation as to why they did not occur according to intended schedule.

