7.2 Biological Sample Submissions

1. Specimens are to be submitted as outlined in Section [Q](#).
2. All specimens submitted must be entered and tracked via the online ECOG-ACRIN Sample Tracking System (STS).

Rev Add2

Biological Materials	Prior to Start of Treatment	Cycle 1, Day 7 (+/- 2 days)	Cycle 2, prior to start of treatment (+/- 1 week)	Cycle 3, prior to start of treatment (+/- 1 week)	Progression
Submit from patients who answer 'Yes' to 'I agree that my tissue and blood samples and related health information may be kept in a Biobank for use in future health research.' ⁵					
Archival Tumor Tissue Biopsy ¹	X				
Plasma (one 10mL EDTA purple top tube) ²	X	X ⁶	X ^{6,7}	X ⁷	
Submit from patients who answer 'Yes' to 'I agree biopsies may be done to obtain research samples.'					
Serial Tumor Tissue Biopsy ^{1,4}	X		X ³		X

1. Tumor tissue and related pathology reports are to be submitted within one month of randomization or collection.
2. Kits are being provided for the collection and shipment of the plasma specimens. See [Appendix VI](#) for instructions. Kit orders will on average be delivered within three (3) business days from when the order was placed.
3. Either week 1 +/- 2 days or week 4 +/- 1 week or both. The investigator will use clinical judgement to choose time points for the second on-treatment biopsy and whether both may be collected.
4. Serial biopsies are to be obtained from patients that have easily accessible lesions.
5. As outlined in the Informed Consent patient participation in tumor tissue and plasma submissions is optional. Institutions must offer participation in these optional studies to all patients.
6. For patients submitting tumor tissue from serial research biopsies plasma collection will be prior to start of treatment, Cycle 1 Day 7 (+/- 2 days, and prior to start of Cycle 2 treatment (+/- 1 week).
7. For patients not submitting tumor tissue from serial research biopsies plasma collection will be prior to start of treatment, prior to start of Cycle 2 treatment (+/- 1 week), and prior to Cycle 3 treatment (+/- 1 week).

Drug Formulation and Procurement

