9.3 Sample Size Considerations and Monitoring Plan

Rev Add2

In patients with elevated LDH, the null hypothesis is a 1-year PFS rate of 20% in the control arm and the targeted effect size is 25% improvement in the treatment arm (i.e. alternate hypothesis is 45% 1-year PFS rate).

Eighty-four patients (for 80 eligible and evaluable) will be equally randomized to HCQ vs. placebo arms. It is expected to accrue 84 patients in 28 months (target accrual 3 patients per month). We expect the number of patients who will be censored before one-year will be very small (less than 4 out of 84 accrued). The sample size of 80 eligible and evaluable patients will provide 81.7% power for the comparison of one-year PFS rate of 20% to 45%. To be conservative, we used the power calculation based on the Fisher's exact test, assuming 80 patients with one-year PFS assessed. One-sided type I error rate of 0.10 was used. It is likely PFS follows a cure rate model with a mixture of patients who have progression and cured. As there is limited data to evaluate the cure rate model parameters, a landmark analysis based on the one-year PFS rate was used for the sample size calculation.

One interim analysis for futility will be conducted when one-year PFS rate is assessed in the first 40 patients at 50% information time. We will adopt a stopping rule proposed by Wieand et al. (Statistics in Medicine vol 13: 1453-1458, 1994). That is, if one-year PFS rate in the HCQ arm is lower than the one-year PFS rate in the placebo arm, an early stopping will be considered. Conditional power will be also estimated.

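### The plan has no scoring rule for a target lesion irradiated on study, so radiation shrinkage can count as response and as freedom from progression at one year

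*Combined protocol and SAP*

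**What the plan says.** **Radiotherapy allowed on study.** Section 3.1.21 states: "Radiotherapy delivered to palliate pain is allowed as long as it is not targeting a lesion that meets RECIST criteria for progression". Sections 3.1.21 and 5.1.6 add: "Gamma knife radiotherapy for known active, asymptomatic small volume CNS lesions may be performed during the first cycle while on study". Section 5.1.6 says how study drugs are held around radiotherapy but not how the treated lesion is then scored.

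**Which lesions are targets.** Section 6.1.2 takes "All measurable lesions up to a maximum of 2 lesions per organ and 5 lesions in total, representative of all involved organs". It makes no exception for lesions in the brain or lesions irradiated before or during the study. On lesions in a previously irradiated area, the same section says: "If the investigator thinks it appropriate to include them, the conditions under which such lesions should be considered must be defined in the protocol". No section supplies those conditions, although prior radiotherapy (3.1.8) and treated brain metastases (note to 3.1.30) are both allowed at entry.

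**How outcomes are scored.** Section 6.1.4.1 defines CR, PR and PD on the target lesions. PR is a fall of at least 30% in their sum from baseline. PD is a rise of at least 20% and 5 mm from the smallest sum on study. The table in 6.1.4.4 has no row for an irradiated or unmeasured target lesion. Section 9.2 defines PFS with no mention of radiotherapy.

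**Scan timing.** Section 6.1 asks for response assessment every 8 weeks. The brain imaging row in 7.1 reads "Every 4 cycles if brain metastases are present on baseline scan, or more often as clinically indicated". A footnote in 7.1 asks for involved visceral areas to be re-imaged every 2 cycles and does not say whether that includes the brain.

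**The concern.** The radiotherapy bar applies only once a lesion already meets progression. A painful target lesion that is growing but has not reached that point may be irradiated, and its diameter stays in the sum. Two outcomes are exposed. For response, radiation shrinkage enters the PR or CR count and is credited to the drug regimen. For the primary endpoint, local treatment can hold the sum below the progression threshold, so a failing patient is counted as event-free at 12 months.

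Response is assessed by the investigator (Section 1.1), so each site would settle these cases in its own way. The trial is small: one patient is 2.5 percentage points of a 40-patient arm.

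**Working it through.** **1. Response, with assumed lesion sizes.** Take two target lesions of 30 mm each, a baseline sum of 60 mm. One is irradiated and falls to 10 mm; the other stays at 30 mm. The sum is 40 mm and the change is (40 − 60)/60 = −33%. That meets the PR criterion with no change in unirradiated disease.

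**2. Progression, with assumed lesion sizes.** With a smallest sum of 60 mm, PD needs 60 × 1.20 = 72 mm. At +15% the sum is 60 × 1.15 = 69 mm, so PD is not met and a painful contributing lesion may be irradiated. If it shrinks, the patient stays progression-free unless a new lesion, growth elsewhere or death occurs.

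**3. The plan's own power.** Inputs from Section 9.3: 80 evaluable patients allocated 1:1, so 40 per arm; one-year PFS 20% v 45%; Fisher's exact test. On alpha: "One-sided type I error rate of 0.10 was used". Exact enumeration of the two binomials gives 0.8169, which reproduces the stated 81.7%. Section 9.4 plans a different primary test, the difference in rates over the square root of the summed variances. With no censoring its exact power is 0.878 and its exact size at 20% v 20% is 0.105.

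**4. Effect of masking.** Let m be the share of true one-year failures recorded as progression-free, equal in both arms. Each rate becomes p′ = p + m(1 − p). The documents give no value for m; 5% and 10% are assumptions.

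| m | Placebo p′ | HCQ p′ | Difference | Fisher power | z-test power | z-test size |
|---|---|---|---|---|---|---|
| 0 | 20% | 45% | 25.0 points | 81.7% | 87.8% | 0.105 |
| 5% | 0.20 + 0.05 × 0.80 = 24% | 0.45 + 0.05 × 0.55 = 47.75% | 23.75 points | 76.9% | 83.6% | 0.109 |
| 10% | 0.20 + 0.10 × 0.80 = 28% | 0.45 + 0.10 × 0.55 = 50.5% | 22.5 points | 72.4% | 79.7% | 0.106 |

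The size column takes both arms at the placebo p′. Equal masking shrinks the difference and costs power; it does not materially raise type I error.

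**5. Scale of the decision.** Against 8/40 event-free on placebo, the planned z-test first becomes significant at 13/40: (0.325 − 0.200)/√(0.325 × 0.675/40 + 0.200 × 0.800/40) = 0.125/0.0974 = 1.284, against a critical value of 1.282. The margin is five patients.

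**6. Scan timing.** Four cycles are 4 × 28 = 112 days, or 16 weeks. Scheduled body scans fall at weeks 8, 16, 24, 32, 40 and 48; scheduled brain scans fall at weeks 16, 32 and 48. A brain target lesion therefore has no scheduled measurement at weeks 8, 24 and 40. Twelve months is 365.25/7 = 52.2 weeks, so week 48 is the last scheduled scan before the landmark on both schedules.

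**The case against.** The permission is narrow. Outside the CNS only pain justifies radiotherapy; growth alone does not. CNS gamma knife is limited to cycle 1 and to small known lesions, while a measurable lesion must reach 10 mm on CT, so the overlap with target lesions is unknown. Radiotherapy to new CNS lesions after cycle 1 is not allowed on study, and new lesions are progression. A masked patient must also avoid new lesions, growth elsewhere and death up to month 12. These limits stand, and they keep the likely frequency down.

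Best response is counted only until non-protocol therapy (6.1.4.4), and such therapy ends protocol treatment (5.7). This is a weaker defence. Radiotherapy that the protocol expressly permits is not clearly non-protocol therapy, and that cut-off governs best response, not PFS. Section 5.8 follows patients to progression even after other therapy starts.

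Randomisation and blinding make equal mis-scoring the natural expectation. That is accepted, and it is why step 4 uses the same m in both arms.

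Some stronger readings are tempting but not supported:

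- **Bias in favour of HCQ.** Two masked patients of 40 in the HCQ arm alone, with no true effect, would raise z-test size from 0.105 to 0.242. Nothing in the documents suggests that masking would differ by arm.
- **An unscanned brain lesion produces a PR.** No text lets an unmeasured target be dropped from the sum; the protocol is silent. Brain scans may also be done more often when clinically indicated, and the two schedules meet at week 48, so the interval alone should hardly move the 12-month rate.
- **Serial biopsy distorts the sum.** Section 7.2 says "Serial biopsies are to be obtained from patients that have easily accessible lesions", but biopsies are optional and no mechanism is shown by which they change a measured diameter.
- **The earlier single-arm trial gives the rate.** Its 5/38 with brain metastases is not a count of irradiated target lesions. Its three patients given local radiotherapy received it after isolated progression, so their events came first and were not masked.

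**Conclusion.** The gap is real and specific: on-study radiotherapy to a target lesion is possible under the plan, and no section says how response or PFS is scored afterwards. The conditions that Section 6.1.2 says must be defined for previously irradiated lesions are also missing. Following the plan as written can record radiation shrinkage as PR or CR and can leave a locally treated patient event-free at one year.

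The size is uncertain because the masked share is assumed. At 5% to 10% in both arms, the loss is about 5 to 9 points of power on the Fisher basis and 4 to 8 points on the planned test, which would still have about 80% power at the 10% share. The likely harm is dilution of the effect and response rates that are hard to interpret, not a false-positive trial. For a blinded phase II proof-of-principle study this is a cheap improvement worth making before any unblinded analysis; it does not invalidate the design.

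**What to change.** Add to Section 6, and to 9.4 for item 3:

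1. A lesion in a previously irradiated field is a target only if growth since that radiotherapy is documented.
2. A target lesion irradiated after baseline is not evaluable for response from that date, so no CR or PR may be first recorded afterwards. New lesions, growth elsewhere and death still count as PFS events.
3. One sensitivity analysis of one-year PFS counts on-study radiotherapy to a target lesion as progression. Item 2 alone leaves such a patient event-free in the primary analysis. This analysis is deliberately severe, since some of these patients would not have progressed.
4. A visit at which a target lesion was not measured cannot be scored CR or PR. Reconcile the 8-week response interval in 6.1, the 4-cycle brain imaging row in 7.1 and the 2-cycle re-imaging note in 7.1.

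Reclassifying brain lesions as non-target is not advised. The 6.1.4.4 table lets PR or SD stand when non-target lesions were not evaluated, and 6.1.4.2 makes progression on non-target disease alone very rare, so a growing brain lesion would become harder to score.

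The cost is a few sentences and one extra analysis. A few patients lose response evaluability. The scoring rules themselves need no added scans, and who may be irradiated does not change.
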